7.6. Special Situations Reports

7.6.1. Definitions of Special Situations

Special situation reports include all reports of medication error, abuse, misuse, overdose, reports of adverse events associated with product complaints, occupational exposure with an AE, pregnancy reports regardless of an associated AE and AE in an infant following exposure from breastfeeding.

Medication error is any unintentional error in the prescribing, dispensing, or administration of a medicinal product while in the control of the health care provider, subject, or consumer.

Abuse is defined as persistent or sporadic intentional excessive use of a medicinal product by a subject.

Misuse is defined as any intentional and inappropriate use of a medicinal product that is not in accordance with the protocol instructions or the local prescribing information.

An overdose is defined as an accidental or intentional administration of a quantity of a medicinal product given per administration or cumulatively which is above the maximum recommended dose as per protocol or in the product labelling (as it applies to the daily dose of the subject in question). In cases of a discrepancy in drug accountability, overdose will be established only when it is clear that the subject has taken the excess dose(s). Overdose cannot be established when the subject cannot account for the discrepancy except in cases in which the investigator has reason to suspect that the subject has taken the additional dose(s).

Product complaint is defined as complaints arising from potential deviations in the manufacture, packaging, or distribution of the medicinal product.

Occupational exposure with an AE is defined as exposure to a medicinal product as a result of one's professional or non-professional occupation.

7.6.2. Instructions for Reporting Special Situations

7.6.2.1. Instructions for Reporting Pregnancies

The investigator should report pregnancies in female study subjects that are identified after initiation of study medication and throughout the study, including the post study drug follow-up period, to the Gilead DSPH using the pregnancy report form within 24 hours of becoming aware of the pregnancy.

Refer to Section 7.3 and the CRF/eCRF completion guidelines for full instructions on the mechanism of pregnancy reporting.

The pregnancy itself is not considered an AE nor is an induced elective abortion to terminate a pregnancy without medical reasons.

Any premature termination of pregnancy (eg, a spontaneous abortion, an induced therapeutic abortion due to complications or other medical reasons) must be reported within 24 hours as an SAE. The underlying medical reason for this procedure should be recorded as the AE term.

A spontaneous abortion is always considered to be an SAE and will be reported as described in Sections 7.1.1 and 7.1.2. Furthermore, any SAE occurring as an adverse pregnancy outcome post study must be reported to Gilead DSPH.

The subject should receive appropriate monitoring and care until the conclusion of the pregnancy. The outcome should be reported to Gilead DSPH using the pregnancy outcome report form. If the end of the pregnancy occurs after the study has been completed, the outcome should be reported directly to Gilead DSPH. Gilead DSPH contact information is as follows:

Email: PPD

and Fax: PPD

Pregnancies of female partners of male study subjects exposed to Gilead or other study drugs must also be reported and relevant information should be submitted to Gilead DSPH using the pregnancy and pregnancy outcome forms within 24 hours. Monitoring of the subject should continue until the conclusion of the pregnancy. If the end of the pregnancy occurs after the study has been completed, the outcome should be reported directly to Gilead DSPH, fax number PPD or email PPD

Refer to Appendix 5 for Pregnancy Precautions, Definition for Female of Childbearing Potential, and Contraceptive Requirements.

7.6.2.2. Reporting Other Special Situations

All other special situation reports must be reported on the special situations report form and forwarded to Gilead DSPH within 24 hours of the investigator becoming aware of the situation. These reports must consist of situations that involve study IMP and/or Gilead concomitant medications, but do not apply to non-Gilead concomitant medications.

Special situations involving non-Gilead concomitant medications does not need to be reported on the special situations report form; however, for special situations that result in AEs due to a non-Gilead concomitant medication, the AE should be reported on the AE form.

Any inappropriate use of concomitant medications prohibited by this protocol should not be reported as "misuse," but may be more appropriately documented as a protocol deviation.

Refer to Section 7.3 and the CRF/eCRF completion guidelines for full instructions on the mechanism of special situations reporting.

All clinical sequelae in relation to these special situation reports will be reported as AEs or SAEs at the same time using the AE CRF/eCRF and/or the SAE report form. Details of the symptoms and signs, clinical management, and outcome will be reported, when available.

8. STATISTICAL CONSIDERATIONS

8.1. Analysis Objectives and Endpoints

8.1.1. Analysis Objectives

The primary objectives of this study are as follows:

- To evaluate the efficacy of switching to TAF 25 mg QD versus continued TDF 300 mg QD in virologically suppressed subjects with chronic HBV as determined by the proportion of subjects with HBV DNA ≥ 20 IU/mL (as defined by the modified US FDA-defined snapshot algorithm) at Week 48
- To compare the safety and tolerability of switching to TAF 25 mg QD versus continuing TDF 300 mg QD in virologically suppressed subjects with chronic HBV at Week 48

The key secondary objectives of this study are as follows:

- To compare the safety of switching to TAF 25 mg QD versus continued TDF 300 mg QD as determined by the percent change from baseline in hip and spine bone mineral density (BMD) at Week 48
- To compare the safety of switching to TAF 25 mg QD versus continued TDF 300 mg QD as determined by the change from baseline in estimated creatinine clearance by Cockcroft-Gault method (eGFR_{CG}) at Week 48

Other secondary objectives of this study are as follows:

- To evaluate the proportion of subjects with HBV DNA < 20 IU/mL and target detected/not detected (i.e. < LLOD) at Week 48 in subjects switched to TAF 25 mg QD versus continued TDF 300 mg QD
- To compare the safety of switching to TAF 25 mg QD for 96 weeks versus continued TDF 300 mg QD for 48 weeks followed by open-label TAF for 48 weeks as determined by the percent change from baseline in hip and spine bone mineral density (BMD) at Week 96
- To compare the safety of switching to TAF 25 mg QD for 96 weeks versus continued TDF 300 mg QD for 48 weeks followed by open-label TAF for 48 weeks as determined by the change from baseline in estimated creatinine clearance by Cockcroft-Gault method (eGFR_{CG}) at Week 96
- To compare the serological response (loss of HBsAg and seroconversion to anti-HBs, and loss of HBeAg and seroconversion to anti-HBe in HBeAg-positive subjects) of switching to TAF 25 mg QD versus continued TDF 300 mg QD at Week 48

- To compare biochemical response (normal ALT and normalized ALT) of switching to TAF 25 mg QD versus continued TDF 300 mg QD at Week 48
- To compare the change in fibrosis as assessed by FibroTest[®] for switching to TAF 25 mg QD versus continued TDF 300 mg QD at Week 48
- To evaluate the comparative open-label efficacy and safety of switching to TAF 25 mg QD from Week 48 through Week 96 in subjects initially randomized to TAF 25 mg QD and in subjects sequentially treated with continued TDF 300 mg QD for 48 weeks and then switched to open-label TAF 25 mg QD at Week 96

The exploratory objectives of this study are as follows:

8.1.2. Primary Endpoint

The primary efficacy endpoint is the proportion of subjects with HBV DNA \geq 20 IU/mL (as determined by the modified US FDA-defined snapshot algorithm) at Week 48.

8.1.3. Secondary Endpoint

The secondary efficacy endpoints are:

- The proportion of subjects with HBV DNA ≥ 20 IU/mL (as determined by the modified US FDA-defined snapshot algorithm) at Week 96
- The proportion of subjects with HBV DNA < 20 IU/mL and target detected/not detected (i.e. < LLOD) at Weeks 48 and 96, as determined by the modified US FDA-defined snapshot algorithm
- The proportion of subjects with HBeAg loss and proportion with seroconversion to anti-HBe at Weeks 48 and 96

- The proportion of subjects with HBsAg loss and proportion with seroconversion to anti-HBs at Weeks 48 and 96
- The proportion of subjects with normal ALT and proportion with normalized ALT (by central laboratory and AASLD criteria) at Weeks 48 and 96
- The change from baseline in fibrosis as assessed by FibroTest[®] at Weeks 48 and 96

The key secondary safety endpoints are:

- The percent change from baseline in hip bone mineral density (BMD) at Week 48
- The percent change from baseline in spine bone mineral density (BMD) at Week 48
- The change from baseline in eGFR_{CG} (measured by Cockcroft-Gault method) at Week 48

The secondary safety endpoints are:

- The percent change from baseline in hip bone mineral density (BMD) at Week 96
- The percent change from baseline in spine bone mineral density (BMD) at Week 96
- The change from baseline in eGFR_{CG} (measured by Cockcroft-Gault method) at Week 96

8.1.4. Other Endpoints of Interest

- The change from baseline in serum markers of bone turnover at Weeks 48, and 96
- The change from baseline in urine markers of renal tubular dysfunction at Weeks 48 and 96
- The effect of treatment on health related to quality of life (via SF-36, CLDQ and WPAI questionnaires) at Weeks 48 and 96

8.2. Analysis Conventions

8.2.1. Analysis Sets

8.2.1.1. Randomized Analysis Set

The randomized Analysis Set includes all subjects who were randomized into the study. This is the primary analysis set for by-subject listings.

8.2.1.2. Efficacy

The primary analysis set for efficacy analysis the Full Analysis Set (FAS), defined as all randomized subjects who receive at least one dose of study drug. Subjects will be analyzed according to the randomized treatment assignment.

8.2.1.3. Safety

The primary analysis set for safety analyses is the Safety Analysis Set (SAS), defined as all randomized subjects who receive at least one dose of study drug. Subjects will be analyzed according to the treatment actually received. All data collected during treatment will be included in the safety summaries. Data collected during treatment free follow up will be summarized or listed separately.

8.2.1.4. Biomarkers

The Biomarker analysis set will include all subjects who have evaluable biomarkers data.

8.2.1.5. DXA

8.2.1.5.1. Hip DXA Analysis Set

The Hip DXA Analysis Set includes all subjects who were randomized and had received at least 1 dose of study drug, and had nonmissing baseline hip BMD values. Subjects will be analyzed according to the treatment they actually received.

8.2.1.5.2. Spine DXA Analysis Set

The Spine DXA Analysis Set includes all subjects who were randomized and had received at least 1 dose of study drug, and had nonmissing baseline spine BMD values. Subjects will be analyzed according to the treatment they actually received.

8.3. Data Handling Conventions

For key secondary safety endpoints, an analysis will be performed using the last observation carried forward (LOCF) method to impute missing data.

[figure not shown]
For other categorical secondary efficacy endpoints, missing data will be handled using a missing = failure approach except for the endpoints of HBV DNA \geq 20 IU/mL and HBV DNA < 20 IU/mL.

For the remaining endpoints, values for missing data will not be imputed, unless specified otherwise

8.4. Multiplicity Adjustments

To control type I error for the assessment of the primary efficacy endpoint and key secondary safety endpoints, the hypothesis testing will be performed in a sequential order. The primary hypothesis of non-inferiority of TAF 25 mg QD vs. TDF 300 mg QD with respect to the proportion of subjects with HBV DNA \geq 20 IU/mL (as defined by the modified US FDA-defined snapshot algorithm) at Week 48 will be tested first. The non-inferiority test will be performed using a two-sided, 0.05 alpha level. If non-inferiority is established, then multiplicity adjustments will be performed for the following endpoints using a fallback procedure {Wiens 2005} in the sequential order given below with a pre-specified two-sided alpha level:

- a) Percentage change from baseline in Hip BMD at Week 48 (alpha = 0.02)
- b) Percentage change from baseline in Spine BMD at Week 48 (alpha = 0.01)
- c) Change from baseline in Creatinine clearance (eGFR_{CG}) at Week 48 (alpha = 0.02)
- d) Superiority test for proportion of subjects with HBV DNA \geq 20 IU/mL at Week 48 (alpha = 0.00)

8.5. Demographic Data and Baseline Characteristics

Demographic and baseline measurements will be summarized using standard descriptive methods by treatment group and overall.

Demographic summaries will include sex, race/ethnicity, geographical region, randomization stratification group, and age.

Baseline data will include a summary of body weight, height, body mass index, HBV DNA level, years positive for HBV, ALT level (\leq ULN, > ULN), previous TDF use and other oral nucleoside/nucleotide treatment experience, previous interferon experience, and HBV genotype by history.

8.6. Efficacy Analysis

8.6.1. Primary Analysis

The primary analysis will be performed when the last subject has completed Week 48 assessments or discontinued prematurely. The primary analysis will consist of a non-inferiority evaluation of efficacy of TAF versus TDF, with respect to the proportion of subjects with HBV DNA \geq 20 IU/mL at Week 48 (as defined by the modified FDA snapshot Algorithm). It will be concluded that TAF is not inferior to the TDF if the upper bound of the two-sided 95% confidence interval of the difference between treatment arms (TAF arm – TDF arm) in the response rate is less than 4% (i.e., a margin of 4% is applied to non-inferiority assessment). The 95% confidence interval will be constructed using the normal approximation method based on stratified Mantel-Haenszel proportions, where stratification factors are HBeAg status (HBeAg positive or negative) and age (\geq 50 or < 50 years).

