Demographic and disease characteristics were generally similar between the TAF and TDF groups in both studies and are representative of patient population of HBeAg-negative subjects in Study GS-US-320-0108 and HBeAg-positive subjects in Study GS-US-320-0110. In both studies the majority of subjects were male (> 60%) and Asian (> 70%). As would be expected based on the 2 distinct study populations, subjects in Study GS-US-320-0108 were older (median age: 47 years; range: 19-80 years) than subjects in Study GS-US-320-0110 (median age: 36 years; range: 18-69 years). Differences in baseline characteristics between the 2 studies included HBV DNA levels (median levels were 5.7 and 7.9 log₁₀ IU/mL for GS-US-320-0108 and GS-US-320-0110, respectively), serum ALT levels (median values were 67 and 85 U/L for GS-US-320-0108 and GS-US-320-0110, respectively), and number of years positive for HBV (6.0 and 4.0 years [median values] for GS-US-320-0108 and GS-US-320-0110, respectively). The distribution of HBV genotypes was similar between treatment groups in both studies with the most common genotypes being C (46.1%), D (24.3%), and B (20.4%).

Efficacy of TAF in Subjects with CHB

Primary Endpoint Analysis

For both studies, the primary efficacy endpoint was the proportion of subjects with plasma HBV DNA < 29 IU/mL at Week 48. Table 1-2 presents HBV DNA outcomes for Studies GS-US-320-0108 {Buti 2016} and GS-US-320-0110 {Chan 2016} for subjects at Week 48. In both studies, similar rates of HBV DNA suppression were achieved in the 2 treatment groups when assessed using the M = F method at Week 48 for the Full Analysis Set (FAS). The percentages of subjects with HBV DNA levels < 29 IU/mL at Week 48 were as follows:

- **Study GS-US-320-0108:** TAF 94.0%, TDF 92.9%; difference in proportions (baseline stratum-adjusted): 1.8%, 95% CI: -3.6% to 7.2%
- **Study GS-US-320-0110:** TAF 63.9%, TDF 66.8%; difference in proportions (baseline stratum-adjusted): -3.6%, 95% CI: -9.8% to 2.6%

In both studies, because the lower bound of the 2-sided 95% CI of the difference (TAF - TDF) in the response rate was greater than the prespecified -10% margin, the TAF group met the primary endpoint of noninferiority to the TDF group.

Table 1-2. GS US 320 0108 and GS US 320 0110: HBV DNA Outcome at Week 48 Using HBV DNA of < 29 IU/mL, Missing = Failure (Full Analysis Set)

	GS-US-320-0108		GS-US-3	320-0110
	TAF 25 mg (N = 285)	TDF 300 mg (N = 140)	TAF 25 mg (N = 581)	TDF 300 mg (N = 292)

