HBV DNA < 29 IU/mL	268 (94.0%)	130 (92.9%)	371 (63.9%)	195 (66.8%)
P-value ^a	0.	47	0.	25
Difference in Proportions (95% CI) ^b	1.8% (-3.6	% to 7.2%)	-3.6% (-9.8	8% to 2.6%)
HBV DNA ≥ 29 IU/mL	7 (2.5%)	4 (2.9%)	183 (31.5%)	88 (30.1%)
No Virologic Data at Week 48	10 (3.5%)	6 (4.3%)	27 (4.6%)	9 (3.1%)
Discontinued Study Drug Due to Lack of Efficacy	0	0	1 (0.2%)	0
Discontinued Study Drug Due to AE/Death	3 (1.1%)	1 (0.7%)	6 (1.0%)	3 (1.0%)
Discontinued Study Drug Due to Other Reasons ^c	6 (2.1%)	4 (2.9%)	19 (3.3%)	6 (2.1%)
Missing Data During Window but on Study Drug	1 (0.4%)	1 (0.7%)	1 (0.2%)	0

a P-value for the superiority test comparing the percentages of HBV DNA < 29 IU/mL was from the CMH test stratified by baseline HBV DNA categories and oral antiviral treatment status strata.

Source: GS-US-320-0108 Week 48 CSR, Section 15.1, Table 12; GS-US-320-0110 Week 48 CSR, Section 15.1, Table 12.

Biochemical Analyses

Table 1-3 presents the proportion of subjects with ALT normalization at Week 48 for both studies (GS-US-320-0108) and (GS-US-320-0110) when determined by central laboratory criteria and by AASLD criteria (upper limit of normal range: \leq 30 U/L for males and \leq 19 U/L for females {Lok 2009, Terrault 2015}), respectively.

For Study GS-US-320-0108, the percentage of subjects with normalized ALT (i.e., ALT > ULN at baseline but within the normal range at Week 48) using the central laboratory criteria was numerically higher for the TAF group compared with the TDF group for all time points from Weeks 4 through 48. When assessed at Week 48, rates of ALT normalization were not significantly different between the 2 treatment groups by the Missing = Failure (M = F) method for the Full Analysis Set (FAS). Using the AASLD criteria, the percentage of subjects with normalized ALT was significantly higher in the TAF group than in the TDF group at for all time points from Week 8 onward using the M = F method.

b Difference in the proportion between treatment groups and its 95% CI were calculated based on the MH proportions adjusted by baseline HBV DNA categories and oral antiviral treatment status strata.

c Discontinuation due to other reasons included subjects who prematurely discontinued study drug due to investigator's discretion, withdrew consent, lost to follow-up, noncompliance with study drug, protocol violation, pregnancy, and study termination by sponsor.

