3. STUDY DESIGN

3.1. Study Treatment Plan and Regimen

This is a randomized, double-blind, multicenter, active-controlled study to evaluate the safety and efficacy of TAF 25 mg QD in virologically suppressed subjects who switch from TDF to TAF compared to continued TDF treatment.

Approximately 460 subjects (with approximately 50% of subjects being \geq 50 years old) will be randomized in a 1:1 ratio (A:B) to receive either TAF 25 mg QD and matched placebo of TDF 300 mg QD or Gilead-provided TDF 300 mg QD and matched placebo of TAF 25 mg QD.

At randomization, subjects will be stratified by screening HBeAg status (HBeAg-negative vs. HBeAg-positive) and age (> 50 or < 50 years).

- Treatment Arm A: approximately 230 subjects administered TAF 25 mg QD and matched placebo of Tenofovir DF (TDF) 300 mg QD
- Treatment Arm B: approximately 230 subjects administered Gilead-provided TDF 300 mg QD and matched placebo of TAF 25 mg QD

The duration of double blind treatment is 48 weeks. All subjects who complete 48 weeks of treatment are eligible for participation in the open label TAF 25 mg extension period for an additional 48 weeks (through Week 96). During the double-blind period, subjects with a confirmed creatinine clearance by Cockcroft Gault Method (eGFR_{CG}) < 50 ml/min, and > 20% decline in eGFR by CKD-EPI (cystatin C) compared to baseline during the study, will be required to undergo dose modification to every other day dosing of study drug. Subjects with confirmed creatinine clearance < 30 mL/min during the double blind phase of the study will have the study drug permanently discontinued. Subjects with confirmed eGFR_{CG} < 50 mL/min will not undergo dose modification to every other day during the open-label TAF 25 mg extension period, nor will treatment be permanently discontinued for confirmed eGFR_{CG} < 30 mL/min during the open-label extension period.

Subjects who permanently discontinue study drug (either prematurely or at the end of study [Week 96]) for reasons other than HBsAg loss with confirmed seroconversion to anti-HBs will be followed every 4 weeks for 24 weeks off treatment or until initiation of appropriate alternative, HBV therapy, whichever occurs first. Use of appropriate, alternative HBV therapy is strongly encouraged.

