8.9. Sample Size

With respect to the primary efficacy endpoint of proportion of suppressed subjects with HBV DNA \geq 20 IU/mL (current assay LLOQ), as determined by the modified US FDA-defined snapshot algorithm, at Week 48, when the sample sizes are 230 (TAF 25 mg arm) and 230 (TDF 300 mg arm), a two-group, large-sample normal approximation test of proportions with a one-sided 0.025 significance level will have 80% power to establish non-inferiority of TAF to TDF. It is assumed that both treatment arms will have subjects who have HBV DNA \geq 20 IU/mL (as defined by the modified US FDA-defined snapshot algorithm) at a rate of 2.4% at Week 48 (based on the rates of suppressed subjects having HBV DNA \geq 29 IU/mL [the LLOQ of assay during those studies] after 48 weeks of treatment from the combined data of studies GS-US-174-0102 and GS-US-174-0103 with the ratio of HBeAg- to HBeAg+ subjects assumed to be 2:1), with a non-inferiority margin of 4%.

The proposed sample size (n = 230 for the TAF 25 mg arm, n = 230 for the TDF 300 mg arm) also provides > 99% power to detect a 1.81% difference in the percentage change from baseline in hip BMD at Week 48 (assuming a 1.47% [SD 2.71%] change from baseline in TAF 25 mg arm and -0.34% [SD 2.83%] change from baseline in the TDF 300 mg arm, with a two-sided $\alpha = 0.05$); a > 99% power to detect a 2.00% difference in the percentage change from baseline in spine BMD at Week 48 (assuming a 1.56% [SD 3.84%] change from baseline in the TAF 25 mg arm and -0.44% [SD 4.14%] change in the TDF 300 mg arm, with a two-sided $\alpha = 0.05$); a 97% power to detect a 4.9 mL/min difference in the change from baseline in eGFR_{CG} at Week 48 (assuming a 1.3 mL/min [SD 13.2] change from baseline in the TAF 25 mg arm and -3.6 mL/min [SD 13.0] change from baseline in the TDF 300 mg arm, with a two-sided $\alpha = 0.05$). These assumptions were derived from an HIV switch study (GS-US-292-0109) due to the unavailability of switch data from TAF HBV studies.

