2.2. Week 48 Analysis (Primary Analysis)

The Week 48 analysis was conducted after the last subject completed the Week 48 visit or prematurely discontinued study drug.

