3.3. Strata and Covariates

Subjects will be randomly assigned to treatment groups via the interactive voice or web response system (IXRS) in a 1:1 ratio using a stratified randomization schedule. Stratification will be based on screening for HBeAg status (HBeAg-negative vs HBeAg-positive) and age (\geq 50 or < 50 years). For statistical analyses, the HBeAg status and age strata recorded in the clinical database will be reclassified using the corresponding baseline value and used for analysis. If the number of subjects in a stratum is too small, the stratum may be combined with other strata for analysis.

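### The one-sided 0.025 level stated for the primary non-inferiority test is only nominal: read plainly, the planned interval keeps the stated power but has an error of about 3.2–3.5%

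*Protocol*

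**What the plan says.** Protocol 8.9, repeated in SAP 1.3, sizes the trial on this basis: "a two-group, large-sample normal approximation test of proportions with a one-sided 0.025 significance level will have 80% power". The inputs are 230 per arm, a 2.4% failure rate (HBV DNA at or above 20 IU/mL) in both arms, and a 4-point margin. Protocol 8.4 sets the same level in two-sided form, 0.05.

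The decision rule is in Protocol 8.6.1 and the synopsis. TAF is non-inferior if the upper 95% limit for TAF minus TDF lies below 4%, and "The 95% confidence interval will be constructed using the normal approximation method based on stratified Mantel-Haenszel proportions", with HBeAg status and age as strata. No small-count correction is mentioned.

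SAP 6.1.1 refers to a separate Week 48 SAP for the details of the primary endpoint. That document is not among those supplied. SAP 2.2 records that the primary analysis is done: "The Week 48 analysis was conducted after the last subject completed the Week 48 visit" or stopped study drug early.

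**The concern.** At 2.4%, 230 patients give 230 × 0.024 = 5.5 expected failures per arm, spread over four strata. With counts this low, a Wald-type variance estimate moves with the estimated difference. When the TAF arm happens to show few failures, the difference and its standard error are both too small. Errors then gather in the tail that declares non-inferiority, and the opposite tail has too few.

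This is the trial's only confirmatory efficacy decision, and under Protocol 8.4 it is the gate to the bone and renal tests. A reader who takes 0.025 at face value would understate the risk of a false non-inferiority conclusion.

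**Working it through.** **Inputs.** 230 per arm, 2.4% in both arms, margin 0.04 and one-sided 0.025 are from Protocol 8.9. For the strata, 8.9 gives the "ratio of HBeAg- to HBeAg+ subjects assumed to be 2:1", and 3.1 plans the trial "with approximately 50% of subjects being" 50 or older. Treating the two factors as independent (my assumption) gives strata of 77/76/38/39 for TAF and 76/77/39/38 for TDF.

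**Step 1: the plan's own figure.** SE = √(2 × 0.024 × 0.976 / 230) = 0.01427. Power = Φ(0.04/0.01427 − 1.96) = Φ(0.843) = 80.0%. The required size is (1.96 + 0.8416)² × 2 × 0.024 × 0.976 / 0.04² = 229.8, so 230. The stated power reproduces.

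**Step 2: exact error without strata.** All pairs of failure counts were enumerated under binomial sampling. The rule was d + 1.96·√[p_T(1−p_T)/230 + p_C(1−p_C)/230] < 0.04.
- TDF 2.4% / TAF 6.4% (true difference equal to the margin): the rule passes in 3.20% of trials.
- The opposite tail misses in 1.83%, so two-sided coverage is 100 − 3.20 − 1.83 = 94.97%.
- 2.4% in both arms: power 79.0%.
- Other TDF rates (assumptions): error 4.11% at 1% and 2.89% at 4%.

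One case shows the mechanism. With 5 TAF and 1 TDF failures, d = 1.74 points and the estimated SE is 1.05 points. The upper limit is 1.74 + 1.96 × 1.05 = 3.8 points, which passes. The true SE at 6.4% / 2.4% is √(0.064 × 0.936/230 + 0.024 × 0.976/230) = 1.90 points.

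**Step 3: four-stratum Mantel-Haenszel.** The weights are w_k = n_Tk·n_Ck/(n_Tk + n_Ck). The variance is Σw_k²[p_Tk(1−p_Tk)/n_Tk + p_Ck(1−p_Ck)/n_Ck]/(Σw_k)², or the same with n−1. There were 2,000,000 simulated trials per scenario (Monte Carlo SE for the error about 0.013 points).

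| Form | Error at 2.4% / 6.4% | Power at 2.4% / 2.4% |
|---|---|---|
| Exact Wald, no strata | 3.20% | 79.0% |
| MH, divisor n | 3.44% | 80.0% |
| MH, divisor n−1 | 3.26–3.28% | 79.3% |
| MH, Sato variance | 3.29% | 79.4% |
| MH, divisor n, HBeAg rates 1.2% / 4.8% (assumed) | 3.49% | 80.5% |
| MH, half-event added in each stratum | 2.1–2.4% | 71–73% |
| Stratified Miettinen-Nurminen | 2.18% | 70.05% |

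Exact unstratified checks of other forms: continuity-corrected Wald 2.13% / 73.1%, Newcombe 2.21% / 69.6%, Farrington-Manning 2.06% / 69.2%, Agresti-Caffo 2.75% / 76.4%. No form tested combines an error of 2.5% or less with power near 80%.

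**The case against.** The strongest reply is that nothing in 8.9 is miscalculated. It declares a large-sample approximation, 80% reproduces, the plain reading of 8.6.1 keeps 79–80%, and 0.025 is the usual nominal level for such a method. The Week 48 SAP may give a different variance, and the Week 48 analysis is finished. Under SAP 6.2.2 the Week 96 repeat concerns a secondary endpoint, with both arms on TAF since Week 48, so no confirmatory decision is left to protect. A score interval would also mostly flag trials in which TAF truly is non-inferior. The discordance (planned interval passes, score interval does not) is 9.8% when both arms are at 2.4%, against about 1.1–1.3% at the margin.

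Most of this stands, and it limits the size of the point. It does not remove the gap between a stated 2.5% and an attained 3.2–3.5% at the plan's own rate. Changing to another tested form would move the shortfall from the error to the power.

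Some stronger readings are not supported:
- *The 80% power is wrong, or the trial is too small.* The lower power figures belong to corrected or score forms, and neither document specifies one.
- *The sponsor uses a corrected variance.* Protocol 1.2.3 reports for Study 0108 a "difference in proportions (baseline stratum-adjusted): 1.8%, 95% CI: -3.6% to 7.2"%, a half-width of (7.2 + 3.6)/2 = 5.4 points, against 5.08 by plain unstratified Wald. In Study 0110 the reported half-width is (9.8 + 2.6)/2 = 6.2 against 6.67, the opposite direction. Both intervals are stratum-adjusted and the stratum sizes are not given, so neither identifies a variance form.
- *The unnamed estimator and the rule "If the number of subjects in a stratum is too small, the stratum may be combined with other strata for analysis" (SAP 3.3) are defects in themselves.* They are at most missing detail, which the Week 48 SAP may supply.

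**Conclusion.** The concern holds in a limited form. Under the plain reading of 8.6.1 and the plan's 2.4% rate, the one-sided error is about 3.2–3.5% instead of 2.5%, an excess of 0.7–1.0 point. Power is as stated.

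A reader might infer that overall type I error is out of control. The documents do not support that. Two-sided coverage is about 95%, and the later tests in Protocol 8.4 are reached only after non-inferiority, so familywise error is not pushed above 5%.

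The result rests on an uncorrected variance, on strata built from the plan's own 2:1 and 50% figures, and on the forms tested. The excess shrinks at higher TDF rates and grows at lower ones. Confidence is medium because the Week 48 SAP was not available. The point is worth considering, but it does not invalidate the planned decision.

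**What to change.** 1. In Protocol 8.9 and SAP 1.3, describe 0.025 as the nominal level and state the attained one-sided error and power for the interval actually used. At 2.4% these are about 3.3% and 79–80% if the variance is uncorrected.
2. Beside the Week 48 result, report a stratified Miettinen-Nurminen interval with the same strata and 4% margin. Label it supplementary, because Week 48 has already been analysed. State in advance that its missing the margin does not overturn the planned decision, since it has only about 70% power at 2.4%.
3. Leave the primary rule, the margin and the sample size unchanged.

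The cost is a few lines of text, one standard software option, slightly more reporting, and a stated error a little less favourable than 0.025. An edit to 8.9 is a protocol modification and needs the ethics submission described in Protocol 9.2.1. SAP section 1 already provides for changes after finalization to be documented in the study report.
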